List of Abbreviations

| | |
|----------|---|
| BSA-F | Physical Activity, Exercise and Sport Questionnaire (Bewegungs- und Sportaktivität Fragebogen) |
| CG | Control group |
| CI | Confidence interval |
| CPS | Control Preference Scale |
| EBPI | Evidence-based patient information |
| EDSS | Expanded Disability Status Scale |
| EQ-5D-5L | EuroQol 5-Dimension 5-Level |
| GLTEQ | Godin Leisure-Time Exercise Questionnaire |
| HAQUAMS | Hamburg Quality of Life in Multiple Sclerosis Scale |
| HADS | Hospital Anxiety and Depression Scale |
| HR | Hazard ratio |
| IG | Intervention group |
| MS | Multiple sclerosis |
| PAM | Patient Activation Measure |
| PwMS | Persons with MS |
| RCT | Randomised controlled trial |
| RIKNO | Risk Knowledge in Relapsing Multiple Sclerosis |
| RMS | Relapsing multiple sclerosis |

1 Introduction

This document has been written based on the study protocol version 1.3 from 16.02.2021. A design paper was published (Krause N, Riemann-Lorenz K, Steffen T, *et al.*, 2021).

1.1 Background and Rationale

Multiple Sclerosis (MS) is an inflammatory and degenerative disease of the central nervous system that affects more than 200,000 people in Germany and mostly young adults. In about 85% of the persons with MS (PwMS), MS first progresses in relapses, later chronically progressive. In addition, considerable neuropsychiatric symptoms such as depression, fatigue and cognitive problems may occur in the course of the disease. Uncertainty and the resulting psychological stress in turn may have a negative effect on MS disease activity.

POWER@MS1 aims to encourage patients with MS to find the best way of dealing with the disease based on evidence-based patient information (EBPI) and a complex behaviour change programme (EBBC programme). The web-based EBBC programme is based on the Artificial Intelligence-based software platform broca® and will serve as a disease accompanying empowerment programme with 16 modules for persons at an early stage of MS.

1.2 Objectives and Endpoints

This study investigates the hypothesis that behavioural and web-based information on immunotherapy decision making, disease management, and lifestyle can reduce the inflammatory disease activity in MS and change patient behaviour.

Clinical endpoints are evaluated by the trial statistician, while endpoints related to health economic aspects of the trial are evaluated by the health economics team and therefore not specified in this SAP. Primary and secondary endpoints are listed in Table 1.

Table 1 Objectives and related endpoints

| | Objective | Endpoint |
|------------------|--|---|
| Primary | To determine whether the EBBC programme reduces inflammatory disease activity in MS and changes patient behaviour. | Time to a new T2-lesion or new relapse. |
| Secondary | To determine the impact of the EBBC programme on patient autonomy and empowerment. | Change in the PAM from baseline to 12 months. |
| | To determine whether the EBBC programme promotes informed decisions on immunotherapy. | Comparison of the CPS after 12 months as well as after reaching the primary endpoint. |
| | To determine the impact of the EBBC programme on quality of life. | Change in the HAQUAMS from baseline to 12 months. Change in the EQ-5D-5L. |

| | Objective | Endpoint |
|--|--|--|
| | To determine whether the EBBC programme reduces anxiety and depression. | Change in the HADS from baseline to 12 months. |
| | To determine whether the EBBC programme leads to an increase in physical activity and a healthy dietary behaviour. | Change in the Readiness to change from baseline to 12 months. Change in GLTEQ from baseline to 12 months. Change in the BSA from baseline to 12 months. Change in food group (Questionnaire of healthy diet) from baseline to month 3 and to 12 month. Change in nutrient intake (myfood24) from baseline to 12 month. |

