1.3 Primary objective and endpoint

To determine the impact of the intervention programme on disease activity, the time to a new relapse or a new lesion on T2-weighted MRI images as surrogate for inflammatory disease activity is used. An experienced, blinded rater will evaluate MRI scans. Participating neurologists will clinically evaluate relapses. The characteristic of the relapse, e.g. duration of complaints, symptoms and degree of impairment, is assessed. In case of relapse or new T2 lesions, the primary endpoint is formally reached. However, study participants were asked to remain in the study.

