2.3 Sample Size

One event (relapse or at least one new T2 lesion) is expected in every second PwMS within 12 month in the CG. The 100 events result in a statistical power of 85% for a two-sided significance level of 5%. The assumed HR of 0.55 represents a reduction of 45% by IG compared with the CG. With a mean observation time of 12 month, the 100 events can be expected to be observed in 262 PwMS. Due to the assumption of 20% drop-outs over 1 year, it was planned to randomise 328 PwMS (164 per group).

The blinded sample size recalculation report dated on 15th September 2021 is based on a blinded data export of August 16th 2021 comprising events of 135 included patients at that time ([name] and [name], 2021). In the first definition of the primary endpoint events, only definite relapses were counted. In the second definition, possible relapses were counted, additionally. The first definition resulted in 46 primary endpoint events, while the second resulted in 51 primary endpoint events. The calculation of event rates according to the first definition and an assumed dropout rate of 20% resulted in 250 PwMS (125 per group) that have to be randomized. The calculation of event rates according to the second definition and an assumed dropout rate of 20% resulted in 216 PwMS (108 per group) that have to be randomized. The blinded sample size recalculation report resumed, that a sample size of at least 240 PwMS should be targeted.

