2.7 Timing of Outcome Assessments

Data is collected over a period of 12 months, with a flexible follow-up of up to 24 months in early recruited PwMS. Several measurement time points for outcome assessment are intended. They are calculated based on the randomization date: t_1 and t_0 take place before randomization; V_1 is scheduled in month 1 (30 days after randomization), V_2 in Month 3 (+90 days), V_3 in Month 6 (+180 days), V_4 in Month 12 (+365 days). For early recruited PwMS, V_5 takes place in Month 18 and V_6 in Month 24. After reaching the primary endpoint, t_x takes place. Deviations from the ideal time point are allowed to the degree of ± 28 days. Table 2 displays the assessment of variables within these time points.

Table 2 Assessments and measurement time points

| Instrument | Measurement time points | | | | | | | | |
|-------------------------------|-------------------------|----------------|----------------|----------------|----------------|----------------|-----------------------------|-----------------------------|----------------|
| | t ₋₁ | t ₀ | V ₁ | V ₂ | V ₃ | V ₄ | V ₅ [*] | V ₆ [*] | t _x |
| Demographic Data | X | | | | | | | | |
| MRI | | X | | X | X | X | X | X | |
| Clinical visit | | X | X | X | X | X | X | X | X |
| Relapse history | | X | X | X | X | X | X | X | X |
| Immunotherapy status | | X | X | X | X | X | X | X | X |
| EDSS | | X | | | | X | | | |
| RIKNO | | | | | X | | | | |
| CPS | | | | | | | X | | X |
| Decision satisfaction | | | | | | | | | X |
| Patient activation | | X | | | | X | | | |
| Emotional coping | | X | | | | X | | | |
| Changes in empowerment | | | | | | X | | | |
| Expectancy | | | X | | | | | | |
| Readiness to change | | X | | X | | X | | | |
| HAQUAMS | | X | | | | X | | | |
| EQ-5D-5L | | X | | | X | X | X | X | |
| HADS | | X | | | | X | | | |
| GLTEQ | | X | | | | X | | | |
| BSA-F | | X | | | | X | | | |
| Questionnaire of healthy diet | | X | | X | | X | | | |
| myfood24 | | X | | | | X | | | |
| Process evaluation | X | X | X | X | X | X | X | X | |
| Health economic parameters | | X | | | X | X | X | X | |

*Only in in early recruited PwMS.

3 Statistical Principles

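### The 12-month CPS endpoint in Table 1 has no month-12 assessment in Table 2, and the superiority framework as written also covers CPS at t_x, which exists only in patients with an event

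*SAP*

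**What the plan says.** Section 1.2, Table 1, gives one endpoint for the objective on informed immunotherapy decisions: "Comparison of the CPS after 12 months as well as after reaching the primary endpoint".

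Section 2.7 places V4 at month 12 (365 days after randomisation) and allows 28 days either side of a visit. On the later visits it says: "For early recruited PwMS, V_5 takes place in Month 18 and V_6 in Month 24". On the event-triggered visit it says: "After reaching the primary endpoint, t_x takes place". In Table 2 the CPS row has two marks, at V5 and t_x. The cells for t0 and V4 are empty.

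Section 2.4 declares a superiority test for every endpoint, without exception. Section 5.2 analyses CPS with a proportional odds model containing intervention and study centre. Neither the text nor the R code says which CPS occasion enters it.

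On patients who have had an event, section 1.3 adds: "However, study participants were asked to remain in the study".

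**The concern.** There are two separate problems.

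The first is a contradiction. Taken literally, Table 2 schedules no CPS at month 12 for anyone, although CPS is the only endpoint for its objective. V5 cannot stand in for month 12: it falls six months later, well outside the 28-day window, and covers early recruits only.

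The second concerns what is tested. The t_x visit exists only for patients with a relapse or new T2 lesion. That is the primary outcome, which the programme is intended to delay. If the programme works, fewer intervention patients reach t_x, and those who do may differ from the control patients who do. The arms at t_x are then subsets selected after randomisation, and a difference in CPS there cannot by itself be read as a programme effect. Because the model names no occasion, the choice between month 12 and t_x also stays open until the data are seen.

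**Working it through.** **Schedule.** The CPS row of Table 2 has the expected nine cells, with marks in the seventh (V5) and ninth (t_x). Two comparisons within the table:

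- Eight other instruments have a 12-month endpoint in Table 1: PAM, HAQUAMS, HADS, readiness to change, GLTEQ, BSA, the healthy diet questionnaire and myfood24. All eight are marked at V4.
- Seven other rows are marked at V5: MRI, clinical visit, relapse history, immunotherapy status, EQ-5D-5L, process evaluation and health economic parameters. All seven are also marked at V4 and V6.

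CPS is the sole exception to both patterns, which suggests that one mark sits in the wrong column.

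**The plan's own figures (section 2.3).** Inputs: "One event (relapse or at least one new T2 lesion) is expected in every second PwMS within 12 month in the CG"; "The assumed HR of 0.55 represents a reduction of 45% by IG compared with the CG"; 85% power; two-sided 5%; 1:1 allocation.

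- Schoenfeld events: 4 × (1.960 + 1.036)² / (ln 0.55)² = 35.9 / 0.357 = 100.5, so 101. With 100 events the power is 84.8%. This agrees with the stated 100 events and 85%.
- Drop-out: 262 / 0.8 = 327.5, so 328, as stated.
- Evaluable N, with the 45% reduction applied to the 12-month proportion: the intervention share is 0.55 × 0.50 = 0.275 and the mean share 0.3875. Then 101 / 0.3875 = 260.6, or 131 per arm, giving the stated 262.
- Evaluable N, with 0.55 taken strictly as a hazard ratio: the intervention share is 1 − 0.50^0.55 = 0.317 and the mean share 0.4085. Then 101 / 0.4085 = 247.3, or 248. The first reading fits the plan's N; both are carried forward.

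**Patients reaching t_x by month 12, original plan, 131 evaluable per arm.**

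- Control: 131 × 0.50 = 65.5, about 66.
- Intervention: 131 × 0.275 = 36.0, to 131 × 0.317 = 41.5, so 36 to 42.
- Total: 101.5 to 107.0 of 262, or 38.7% to 40.8%.
- Control share of the t_x subset: 65.5 / 101.5 = 64.5%, to 65.5 / 107.0 = 61.2%.

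**Whether these rates carry over to the recalculated size.** They do not. The blinded review concluded that "a sample size of at least 240 PwMS should be targeted". With 20% drop-out, 240 × 0.8 = 192. At the original rates that yields only 192 × 0.3875 = 74 to 192 × 0.4085 = 78 events. The recalculated totals of 250 and 216 leave 200 and 172.8 patients after 20% drop-out. If the target is still 100 events (an assumption, since section 2.3 does not restate it), the pooled event share is 100 / 200 = 50% to 100 / 172.8 = 58%. That share may include follow-up beyond month 12.

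The imbalance keeps its direction at these higher shares. At a pooled 57.9% with hazard ratio 0.55, the arm shares are about 68.6% and 1 − 0.314^0.55 = 47.1%, so the control arm supplies 0.686 / 1.157 = 59% of the subset. With the 45% reduction applied to proportions it supplies 1 / 1.55 = 65%.

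**The case against.** The strongest reply is that the empty V4 cell is a typing slip with little consequence. Table 1 states the endpoint clearly, the pattern of the other rows shows where the mark belongs, and the protocol on which the SAP is based would govern collection. A shift of this one cell when the PDF was read cannot be fully excluded either, although the cell count is right and neighbouring rows align. Most of this stands. A reader might infer that the 12-month CPS was never collected or that the objective is lost; the document does not support that. What remains is that the two tables disagree and no other section resolves it.

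On t_x, asking about the decision role after new disease activity is a sensible purpose, the conditioning is visible in Table 1's own wording, and CPS is neither the primary endpoint nor the key secondary one (section 1.4 gives that place to HAQUAMS). This limits the weight of the point but does not remove it, because section 2.4 makes no exception for t_x. Nor would a baseline CPS in the model have cured the problem: it would not restore randomisation in a subset selected by an event.

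A reader might also infer from section 5.3 that t_x values would be imputed for event-free patients. The SAP does not say so. That section concerns missing assessments, and without an event the t_x value is undefined, not missing.

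**Conclusion.** Both parts hold in limited form. Tables 1 and 2 contradict each other on the 12-month CPS, probably through one misplaced mark. As written, the superiority framework also covers a t_x comparison that randomisation does not protect.

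Under the original planning values about 66 control against 36 to 42 intervention patients would reach t_x by month 12, roughly 39% to 41% of 262. This assumes full 12-month follow-up of the evaluable patients and, for the upper figure, proportional hazards. The recalculation points to a larger subset, about 50% to 58% if 100 events is still the target, and follow-up of up to 24 months in early recruits would add to it. It is tempting to read these counts as the size of a bias. They show only that the subsets are unequal and selected by outcome. Any bias in CPS is unknown and may be small.

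The primary analysis and the sample size are unaffected. The point should be settled before the CPS data are analysed.

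**What to change.** - Check the CPS row of Table 2 against what was collected and reconcile it with Table 1. If the 12-month CPS was collected, mark V4. If it was not, state that the endpoint is unavailable at 12 months and that V5 covers early recruits only.
- In section 5.2, state that the proportional odds superiority test uses the 12-month CPS in all randomised patients. This is feasible because section 1.3 asks patients with an event to stay in the study.
- In section 5.2, state that the t_x CPS is reported by arm descriptively, labelled as conditional on a primary endpoint event, with no claim of a treatment effect.

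The cost is one table cell and two sentences. The downside is that one secondary test becomes descriptive.

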1.3 Primary objective and endpoint

To determine the impact of the intervention programme on disease activity, the time to a new relapse or a new lesion on T2-weighted MRI images as surrogate for inflammatory disease activity is used. An experienced, blinded rater will evaluate MRI scans. Participating neurologists will clinically evaluate relapses. The characteristic of the relapse, e.g. duration of complaints, symptoms and degree of impairment, is assessed. In case of relapse or new T2 lesions, the primary endpoint is formally reached. However, study participants were asked to remain in the study.

1.4 Secondary objective and endpoint

Key secondary endpoint is quality of life measured by the HAQUAMS. Secondary endpoints are given in Table 1. For further details on the definition of the endpoints, see Section 5.1.

2 Study methods

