2.4 Framework

All endpoints are tested for superiority of the intervention programme over control.

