3.1 Confidence intervals and p-values

All tests will be performed two-sided with 5% significance level. Confidence intervals (CI) will be reported with 95% confidence level.

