# plot KM curve
plot(survfit(cox.regr))
km.by.treat <- survfit(SurvObj ~ intervention, data = primEndpoint,
                        conf.type = "log-log")
```

Secondary endpoints will be analysed using group mean comparisons between the intervention groups (δ) adjusted for baseline assessments and centre in analysis of covariance (ANCOVA) models. Least square group differences will be reported with 95% CIs and p-values testing the null hypothesis of no intervention effect ($H_0: \delta = 0$).

```

library(emmeans)

mod.sec <- lm(var ~ intervention + var_baseline + site,
               data = secEndpoints)

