# report least square group differences
tmt.means <- emmeans(mod.sec, ~ intervention)
tmt.means
pairs(tmt.means)

```

Additionally, longitudinal assessed endpoints will be analysed using Gaussian linear models for repeated measures with intervention group, time, intervention-by-time interaction and study centre as factors and baseline score as a covariate (mixed model for repeated measurements, MMRM). The error terms are assumed to follow a multivariate normal distribution with unstructured covariance matrix. Least square group differences will be reported with 95% CIs and p-values testing the null hypothesis of no intervention effect ($H_0: \delta = 0$).

```

library(lme4)
library(car)
library(emmeans)

mod.sec <- lmer(var ~ baseline_var + intervention + time + intervention * time +
                 site + (1|Patient.Id), data = secEndpoints)
summary(mod.sec)
res <- Anova(mod.sec, type = "III", test.statistic = "F")
res
tmt.means <- emmeans(mod.sec, ~ intervention * time)
pairs(tmt.means)

```

For the Readiness to Change and the Control Preference Scale, ordinal regression with logit link (proportional odds model) will be used with intervention, study centre as covariates and for readiness to change the baseline value. The model assumption will be checked.

```

library(ordinal)
library(emmeans)

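### HAQUAMS is named key secondary endpoint, but every endpoint is tested for superiority at an unadjusted two-sided 5%, so the label has no inferential function

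*SAP*

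**What the plan says.** Section 1.4 gives HAQUAMS its rank: "Key secondary endpoint is quality of life measured by the HAQUAMS". The rank appears nowhere else. Table 1 in Section 1.2 lists HAQUAMS beside the EQ-5D-5L under the quality-of-life objective ("Change in the HAQUAMS from baseline to 12 months. Change in the EQ-5D-5L"), as one of ten secondary instruments and without distinction.

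Two sentences fix the testing framework. Section 2.4: "All endpoints are tested for superiority of the intervention programme over control". Section 3.1: "All tests will be performed two-sided with 5% significance level".

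Section 5.2 then sets out the models. "Secondary endpoints will be analysed using group mean comparisons between the intervention groups", adjusted for baseline and centre, each with a 95% CI and a p-value against no effect. HAQUAMS falls under this common ANCOVA. Readiness to change and the CPS have ordinal models, and nutrient intake has a mixed model. Endpoints measured repeatedly get a further analysis: "Additionally, longitudinal assessed endpoints will be analysed using Gaussian linear models for repeated measures".

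The SAP contains no testing order, gatekeeping rule, alpha split or multiplicity adjustment, and no statement that any secondary endpoint is exploratory. The word unadjusted is not the SAP's. It follows from the single 5% level in Section 3.1 and the absence of any adjustment elsewhere.

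**The concern.** Naming a key secondary endpoint normally tells the reader which secondary result may carry a claim of its own and under what condition. Here Section 1.4 creates a hierarchy, and Sections 2.4 and 3.1 treat all endpoints alike. A HAQUAMS result at p < 0.05 would have the same formal standing as the same p-value for the diet score.

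Leaving secondary endpoints unadjusted is usually defended by calling them supportive or exploratory. This SAP describes them all as superiority tests, so that defence is not written down. At stake is how secondary results are read, above all if the primary test is not significant and one of the many secondary p-values falls below 0.05.

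**Working it through.** **1. The SAP's own figure.** Section 2.3 states 85% power from 100 events at HR 0.55 and two-sided 5%. By Schoenfeld's formula, z = (√100 / 2) × |ln 0.55| − 1.96 = 5 × 0.598 − 1.96 = 1.03, which gives 84.8% power. The figure reproduces. It shows that the full two-sided 5% is spent on one primary test. The SAP states no familywise error rate for the secondary endpoints, so there is nothing further to reproduce.

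**2. Number of secondary tests (Table 1 and Section 5.1).**

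| Instrument | One per instrument | Subscales, behaviours and time points separate |
|---|---|---|
| PAM | 1 | 1 |
| CPS (12 months; after the primary endpoint) | 1 | 2 |
| HAQUAMS | 1 | 1 |
| EQ-5D-5L | 1 | 1 |
| HADS (anxiety; depression) | 1 | 2 |
| Readiness to change (diet; activity) | 1 | 2 |
| GLTEQ | 1 | 1 |
| BSA | 1 | 1 |
| Healthy diet (3 and 12 months) | 1 | 2 |
| myfood24 (one nutrient) | 1 | 1 |
| Total | 10 | 14 |

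The SAP fixes no upper limit. The EQ-5D-5L yields an index and a 0 to 100 rating, the GLTEQ and BSA yield several scores, the nutrients of interest are not listed, and the repeated-measures model adds further p-values.

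**3. False-positive chance if no secondary effect is real.** For k independent tests:
- significance in either direction: 1 − 0.95^k
- significance in favour of the intervention (2.5% per test): 1 − 0.975^k

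For k = 10: 1 − 0.95^10 = 40.1% and 1 − 0.975^10 = 22.4%.
For k = 14: 1 − 0.95^14 = 51.2% and 1 − 0.975^14 = 29.8%.

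**4. Effect of correlation.** The SAP gives no correlations, so a common correlation r between test statistics (scored so that higher favours the intervention) is an assumption. Normal simulation with 400,000 draws:

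| k | Direction | r = 0 (formula) | r = 0.3 | r = 0.5 | r = 0.7 |
|---|---|---|---|---|---|
| 10 | either | 40.1% | 35.0% | 28.8% | 21.4% |
| 10 | favouring intervention | 22.4% | 17.8% | 14.4% | 10.7% |
| 14 | either | 51.2% | 43.9% | 34.9% | 25.0% |
| 14 | favouring intervention | 29.8% | 22.4% | 17.4% | 12.5% |

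The lowest directional figure, 10.7%, is still more than four times the nominal 2.5% (10.7 / 2.5 = 4.3).

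**5. What an order would achieve.** Tested side by side at 5%, the primary endpoint and HAQUAMS would have a joint error of 1 − 0.95² = 9.75% if independent and both nulls hold. In a fixed sequence, a false HAQUAMS rejection first needs a significant primary test. If the primary null is true, any false rejection in the pair requires the primary test to reject, which has probability at most 5%. If the primary null is false, only the HAQUAMS test can err, again at most 5%. The pair is held at 5% and the primary test and its sample size do not change.

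**The case against.** The strongest reply is that this is a trial with one primary endpoint, whose error rate is intact and on which alone the sample size rests. Secondary results in such trials are commonly read as supportive. Naming HAQUAMS in advance also has some value, because a reader can see that this scale, and not whichever one reached p < 0.05, was put first. Both points stand. They limit the concern to how secondary results are interpreted, and to the label's inferential function, not its descriptive use.

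Two stronger readings are tempting, and the SAP does not support either.

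- A reader might infer that a false superiority claim among the secondary endpoints is likely. The figures of 40% and 51% count results in either direction, including those favouring control. In the direction of superiority they are 22% and 30% at most for these counts, and lower with positive correlation. All of them assume no true secondary effect at all.
- A reader might infer that any secondary p < 0.05 meets a definition of superiority laid down in the SAP. There is no such definition. Section 2.4 states the type of hypothesis, Section 3.1 the level, and Section 5.2 the reporting of estimates, CIs and p-values. None says that a nominal secondary result will be claimed as proof.

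It might also be said that a multiplicity rule could stand in the protocol, which is not shown. But the SAP does not leave the subject open: Sections 2.4 and 3.1 set one framework for all endpoints, and that framework does not fit the rank given in Section 1.4.

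**Conclusion.** The point holds in this form: HAQUAMS is called key secondary, yet the stated framework gives it the same unadjusted two-sided 5% superiority test as every other endpoint, with no order, adjustment or exploratory status, so the label does no inferential work. With no real secondary effect, the chance of at least one false-positive secondary result is about 40% (10 tests) to 51% (14 tests) under independence, or about 22% to 30% in favour of the intervention. Over assumed correlations of 0.3 to 0.7 the directional figure is about 11% to 22%. These sizes depend on how the tests are counted, and the SAP does not fix that count. The primary conclusion is not affected. This is a cheap improvement worth making, not a flaw in the trial's main inference.

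**What to change.** In Section 3.1, state that the HAQUAMS total score at 12 months, analysed by the ANCOVA of Section 5.2, is tested as confirmatory at two-sided 5% only if the primary Cox test is significant. In Section 2.4, limit the superiority claim to the primary endpoint and HAQUAMS, and say that all other secondary endpoints are reported with estimates, 95% CIs and nominal p-values as exploratory.

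This needs no further data, no larger sample and no alpha from the primary test. It should be fixed before results by treatment group are known. The cost is that HAQUAMS cannot be claimed as confirmatory if the primary test fails, and that the other secondary endpoints lose any confirmatory reading.

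If that cost is unwelcome, dropping the key label and declaring all secondary p-values nominal and exploratory would also remove the inconsistency, but would leave no confirmatory secondary endpoint. A Bonferroni split over ten secondary tests would put each at 0.05 / 10 = 0.005, which is a heavier price.
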